Participants

The initial sample of respondents (n=350) was recruited through an open project application lasting two months (from 1 July 2021 to 1 September 2021), from which 300 preschool children aged 4–7 were selected for this randomized, controlled intervention study. The recruitment process was completed after the selection process, and the optimal sample of subjects was filled out. The study sample underwent stratified randomization, resulting in the division into either EG (Experimental Group - 1) or CG (Control Group - 2). When stratifying, researchers used proportionate sampling to maintain the correct proportions of genders in every group. The intervention program started with a group of 150 children in EG, and at the same time, 150 children in CG started a kindergarten educational program in a Preschool Institution. Throughout the nine months of the experimental program, 51 children from the intervention group and 29 from the control group were excluded from the final analyses due to injury, flu, illness, or attendance at classes falling below 80%. Finally, 99 children (54 boys & 45 girls) who composed the EG and 121 children (64 boys & 57 girls) who composed the CG were analyzed for the effects of the DG. After nine months, a total of 220 participants were included in the final analysis. The parents or guardians of each child provided written informed consent, and the study received approval from the institutional ethics committee at the Faculty of Sport and Physical Education, University of Novi Sad (ethical approval number: 46-06-04/2020-1).

[figure not shown]
The exclusion criteria were:

- History of neurological or musculoskeletal disorders
- Clinical conditions that could affect balance, such as motor disorders, diabetes, heart disease, stroke, vision problems, thyroid issues, or issues with nerves or blood vessels.

The inclusion criteria for this study were:

- No injuries within the past six months
- No other medical conditions, including COVID-19
- No scheduled physical activity in the previous three months
- Considered valid for the experimental programs if participants completed at least 80% of all training sessions.

Figure 1 illustrates the flow of participants through the study.

Testing procedures

Secondary outcome – Anthropometric measures

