In contrast, the CG adhered to their routine, engaging in three structured extracurricular physical activity sessions per week, each lasting approximately 45 minutes. A physical education specialist and a kindergarten teacher led these sessions. They were designed to enhance fundamental locomotor skills (e.g., hopping, skipping, jumping, crawling, and navigating obstacles) and manipulative skills involving balls, bricks, and toys. The primary objective was to create an environment where children could enjoy and have fun during exercise. According to the National Program for Kindergarten Physical Education Classes, the standardized program predominantly featured frontal and group activities, encompassing traditional games and dances, and included different training forms. The authors did not thoroughly provide detailed information about the intervention program.

Statistical analyses

Unless otherwise specified, we present data as mean and 95% confidence intervals [95% CIs]. We conducted an independent samples t-test to examine whether the baseline study outcomes varied among the groups. Normality was confirmed using the Kolmogorov-Smirnov test, and homogeneity of variances and covariance matrices were accepted through Levene's and Box's tests, respectively. We first modelled raw scores of each study outcome using a 2x (girls vs. boys), 2x (EG vs. CG), and 2 (initial vs. final testing) mixed ANCOVA (Model 1) to test confounding effects of gender, age, and BMI on intervention effects. We inspected the main effects of gender, age, and BMI to assess whether the study outcomes depended on these factors. This examination aimed to determine whether gender, age, and BMI could control the effects of the DG program on the study outcomes. Hence, respecting the significance of control variables effects ($p \leq 0.05$), we modelled each study outcome using either a 2x (girls vs boys) 2x (EG vs CG) 2 (initial vs final testing) mixed ANCOVA with age and BMI or only with age to find whether study outcome mean changes [95% CIs] from initial to final testing depended on whether subjects completed DG program or not (Model 2). We assessed potential gender confounding effects on changes in the study outcomes by

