examining a time*group*gender interaction effect, followed by a time*group interaction effect for boys and girls, respectively. The time*group interaction effects allowed the evaluation of DG program effects followed by the simple main effects of time, which designated mean changes [95% CIs] from initial to final testing for each group. In addition, we estimated the parameters (beta coefficients, β and partial η^2 , η^2) of ANCOVA models. Games-Howel tests corrected multiple comparisons, and a p-value of ≤ 0.05 designated statistical significance. Partial eta squared (partial η^2) is reported as a measure of effect size and classified as small (0.01), medium (0.06), and large (0.14), according to Cohen. We conducted all analyses using SPSS (v.23, IBM Corporation, New York, USA).

References

Bala, G. (1996). *Sportska školica - Razvoj motoričkog ponašanja dece* (Sports school - Development of children's motor behavior). Kinesis.

Butler, L. S., Sugimoto, D., Erdman, A., Yoder, J., Greiner, K., Larroque, C., Latz, K., Loewen, A., Wyatt, C. W., DeVerna, A., & Ulman, S. (2023). Highly Active Middle School Athletes Demonstrate Poor Motor Skill Proficiency. *Sports Health*, 19417381231178822. <https://doi.org/10.1177/19417381231178822>

Lopes, V. P., Saraiva, L., & Rodrigues, L. P. (2018). Reliability and construct validity of the test of gross motor development-2 in Portuguese children. *International Journal of Sport and Exercise Psychology*, 16(3), 250-260. <https://doi.org/10.1080/1612197X.2016.1226923>

Nagy, Á., Wilhelm, M., Győri, F., Domokos, M., & Berki, T. (2023). Assessment Tools Measuring Fundamental Movement Skills of Primary School Children: A Narrative Review in Methodological Perspective. *Sports*, 11, 178. <https://doi.org/10.3390/sports11090178>

Radanovic, D. (2018). *The effects of the developmental gymnastics program on the development of motor skills and abilities and morphological characteristics of preschool children* University of Novi Sad]. Novi Sad.

Ulrich, D. (2000). *Test of gross motor development-2*.

UNIVERSITY OF NOVI SAD
FACULTY OF SPORT AND PHYSICAL EDUCATION
ETHICS COMMITTEE – COMMISSION

DECISION No. 46-06-04/2020-1

ETHICS COMMITTEE - COMMISSION FOR THE IMPLEMENTATION OF SCIENTIFIC
PROJECT - RESEARCH

DESCRIPTION

After reviewing the submitted application (on June 17, 2020) for a scientific research project entitled: **Biomechanical parameters of athlete's postural stability**

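### The small/medium/large labels for the time*group partial eta squared depend on the initial-final correlation, so they do not measure the size of the programme effect on the scale the cut-offs come from

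*Protocol*

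**What the plan says.** All of this is in the protocol's Statistical analyses section, except the sample, which is under Participants. No separate statistical analysis plan is at hand, and the point rests only on what the protocol states.

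- **Model.** "We first modelled raw scores of each study outcome using a 2x (girls vs. boys), 2x (EG vs. CG), and 2 (initial vs. final testing)" opens the description of Model 1, a mixed ANCOVA. Model 2 is a "mixed ANCOVA with age and BMI or only with age to find whether study outcome mean changes [95% CIs] from initial to final testing".
- **Effect that carries the comparison.** "The time*group interaction effects allowed the evaluation of DG program effects followed by the simple main effects of time". The mean changes and 95% CIs that follow are given per group.
- **Effect-size grading.** Partial eta squared "is reported as a measure of effect size and classified as small (0.01), medium (0.06), and large (0.14), according to Cohen". Nothing separates within-child effects such as time*group from between-child effects.
- **Significance.** "a p-value of ≤ 0.05 designated statistical significance".
- **Analysed sample.** "Finally, 99 children (54 boys & 45 girls) who composed the EG and 121 children (64 boys & 57 girls) who composed the CG were analyzed".

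The protocol states no initial-final correlation, no SD and no standardised mean difference.

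**The concern.** Grading cut-offs have meaning only on the scale for which they were set. The values 0.01, 0.06 and 0.14 express a difference between independent groups relative to the spread between children. With two test occasions, the time*group effect is the difference between arms in change, and its partial eta squared compares that difference with the spread of change. The two spreads agree only at one particular initial-final correlation.

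The same programme benefit can therefore be called small, medium or large according to how stable the outcome is over time. The grading covers every outcome: single skills scored on a few pass/fail criteria, subtest totals, and the anthropometric measures. There is no reason to expect one common correlation for these, so labels could rank outcomes by stability as well as by programme effect. Partial eta squared is the only graded measure in the protocol, so readers are likely to take their impression of the benefit from it.

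**Working it through.** **Inputs.** From the protocol: cut-offs 0.01, 0.06 and 0.14; 99 and 121 children analysed; two occasions; time*group as the effect of interest. Assumed, because the protocol does not give them: r from 0.3 to 0.9, equal SD at both occasions, and R², the share of the variance of change explained by covariates, from 0 to 0.2.

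**Step 1: reproduce the cut-offs.** For two equal independent groups, eta² = d²/(d² + 4).
- d = 0.2: 0.04/4.04 = 0.010
- d = 0.5: 0.25/4.25 = 0.059
- d = 0.8: 0.64/4.64 = 0.138

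These round to the protocol's 0.01, 0.06 and 0.14, so the cut-offs sit on the between-child SD scale. The unequal arms hardly matter. With pq = 99 × 121/220² = 0.2475, against 0.25 for equal arms, the cut-offs correspond to d = 0.20, 0.51 and 0.81.

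**Step 2: partial eta squared for time*group.** With two occasions, the time*group F is the F for group on the change score. In units of the between-child variance, change has variance 2(1 − r). Let d be the between-arm difference in change in between-child SD units. Then

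x = d² × pq / [2(1 − r)(1 − R²)], and partial eta² = x/(1 + x).

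At r = 0.5 and R² = 0 the divisor is 1 and the two scales coincide.

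**Step 3: one benefit, several labels.** Take d = 0.4, R² = 0, so d² × pq = 0.16 × 0.2475 = 0.0396.
- r = 0.3: x = 0.0396/1.4 = 0.0283; partial eta² = 0.028 (small)
- r = 0.5: x = 0.0396/1.0; partial eta² = 0.038 (small)
- r = 0.7: x = 0.0396/0.6 = 0.066; partial eta² = 0.062 (medium)
- r = 0.8: x = 0.0396/0.4 = 0.099; partial eta² = 0.090 (medium)
- r = 0.9: x = 0.0396/0.2 = 0.198; partial eta² = 0.165 (large)

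**Step 4: where each label starts.** Solving for d at cut-off e gives d = √{[e/(1 − e)] × 2(1 − r)/pq}. For e = 0.14 and r = 0.8: √(0.1628 × 0.4/0.2475) = 0.51.

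| r (assumed) | small from d = | medium from d = | large from d = |
|---|---|---|---|
| 0.3 | 0.24 | 0.60 | 0.96 |
| 0.5 | 0.20 | 0.51 | 0.81 |
| 0.7 | 0.16 | 0.39 | 0.63 |
| 0.8 | 0.13 | 0.32 | 0.51 |
| 0.9 | 0.09 | 0.23 | 0.36 |

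**Step 5: covariates.** They enter only through R². At r = 0.7 and d = 0.4, R² = 0.2 moves partial eta² from 0.062 to 0.076. A simulation (400 runs, 99 and 121 children, d = 0.4) used an age covariate that predicts level but not change. Mean partial eta² was 0.096 both without and with age at r = 0.8, and 0.042 both ways at r = 0.5. These means lie slightly above the formula values of 0.090 and 0.038, as expected from the small upward bias of a sample partial eta squared.

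**The case against.** Four points on the other side have force.

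1. **Direction.** A reader might infer that the grading overstates the benefit. The protocol does not support that as a general statement, because it gives no r. Values above 0.5 are plausible: raw scores across ages 4–7 carry stable differences due to age, and the protocol describes the TGMD-2 as reliable. Values below 0.5 cannot be ruled out, least of all for single skills with only three to five criteria each. At r = 0.3 the labels are too strict.
2. **Covariates.** A reader might infer that adjusting for age or BMI in itself inflates the time*group value. It does not. Effects on level go to the between-child error; only effects on change matter. The protocol screens covariates by their main effects, which concern level, and the two versions of Model 2 differ only in whether BMI is included. A different covariate set is therefore, at most, a secondary reason for labels to differ.
3. **Other measures of size.** Partial eta squared is the only graded measure but not the only measure. Means and per-group mean changes with 95% CIs are reported, as are beta coefficients. However, the intervals on change are named per group, and no between-arm difference with its CI is named.
4. **Significance and the 'small' label.** Any time*group result reaching p = 0.05 has partial eta² of at least 0.018 overall (F(1,214) = 3.885; 3.885/217.885). A reader might blame the repeated measures for this. It reflects sample size: a plain comparison of 99 with 121 children at p = 0.05 gives 3.88/(3.88 + 218) = 0.0175.

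None of this removes the dependence of the label on r.

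**Conclusion.** The point holds as one of interpretation. Applied as written, the grading gives labels that reflect initial-final stability as well as programme effect. Over r = 0.3 to 0.9, the effect needed for 'medium' runs from d = 0.60 down to 0.23, and for 'large' from 0.96 down to 0.36. A benefit of d = 0.4 can receive any of the three labels. On the between-child scale the labels are right only near r = 0.5, too high above it and too low below it, and they should not be compared between outcomes whose r differs.

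These figures assume equal SDs at the two occasions and covariates that explain none of the change. The protocol gives nothing that fixes r, so neither the direction nor the size of the distortion in this trial can be stated. The F tests, p-values and mean changes stand as they are. The matter is worth correcting before results are described, because the label is the only graded statement of how large the effect is.

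**What to change.** - Do not grade the time*group partial eta squared as small, medium or large. It may stay as an ungraded statistic.
- For each outcome, report the adjusted between-arm difference in change with its 95% CI in raw points, and the same difference divided by the pooled SD of the initial score.
- Base statements about the size of the effect on that difference.

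This needs only data already collected and a few extra lines of analysis. The downside is that some effects may receive a less favourable description. The standardised value is also relative to the age mix of this sample, which is why the raw-point difference should stand beside it.
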